#### 1. Introduction

This Statistical Analysis Plan is based on Version 6 of the protocol, dated 05May2022. All references to the protocol refer to Version 6.

Nusinersen is an antisense oligonucleotide administered intrathecally via lumbar puncture (LP); it increases survival motor neuron (SMN) protein expression and significantly improves motor function in patients with spinal muscular atrophy (SMA). Nusinersen was approved for the treatment of SMA under the tradename SpinrazaTM in the United States (US), European Union, and other countries. The population for this study includes participants with infantile-onset and later-onset SMA.

Efficacy and safety results across the nusinersen clinical development program have demonstrated an overall positive benefit-risk profile of nusinersen across a broad range of SMA phenotypes and patient populations. Nusinersen is approved in the US, Europe, and other countries and regions for the treatment of SMA in paediatric and adult patients at a recommended dosage of 12 mg administered in 3 loading doses at 14-day intervals, a fourth loading dose 30 days after the third dose, and maintenance doses every 4 months thereafter in most countries and regions. Pharmacokinetic (PK) and pharmacodynamic (PD) analyses indicate that nusinersen drug exposure higher than that achieved with 12 mg in patients with SMA may produce an even greater benefit in motor function. Additionally, PK modelling and simulations identified dosing regimens that achieve higher drug exposure more rapidly. Therefore, this study is being conducted to investigate the efficacy, safety, tolerability, **maintenance** of a 50/28-mg dose of nusinersen (50-mg loading dose/28-mg maintenance dose) and a dosing regimen targeted to achieve higher drug exposure more rapidly. This study will be conducted in participants with genetically confirmed SMA.

This is a 3-part study Part A, Part B (infantile-onset and later-onset), and Part C.

Part A was an open label safety evaluation in which later-onset SMA subjects received 3 loading doses of 28 mg of nusinersen and 2 maintenance doses of 28 mg. All 6 participants enrolled in Part A completed the study.

In Part B, in order to evaluate the proposed higher dosing regimen, an active-controlled design is being used, with participants randomized either to the investigational dosing regimen (50-mg loading/28-mg maintenance) or to the currently approved dosing regimen (12-mg loading/12-mg maintenance). In order to supplement the number of participants available for the analysis in Part B of this study, historical data from the existing data set for Study CS3B, a Phase 3 efficacy and safety study of nusinersen in participants with infantile-onset SMA, may be borrowed to augment the control arm.

Part C of the study will allow safety evaluation of transitioning participants who are on the currently approved dose of nusinersen (12-mg maintenance for at least 1 year after the initiation of treatment) to the proposed higher dosing regimen via the administration of a single bolus dose

Product: Nusinersen	Statistical Analysis Plan
Study: 232SM203	Version: 1.0 Final

of 50 mg of nusinersen (which should be administered 4 months  $\pm$  14 days after their most recent maintenance dose of 12 mg), with maintenance dosing at 28 mg thereafter.

This SAP will cover the planned analysis of Part C.

#### 2. Study Overview

#### 2.1. Study Objectives and Endpoints

#### **Study Primary Objective (Part C)**

To examine the safety and tolerability of nusinersen administered intrathecally at higher doses to participants with SMA.

#### **Study Primary Endpoints (Part C)**

- Incidence of adverse events (AEs), including serious adverse events (SAEs)
- Shifts from baseline in clinical laboratory parameters, electrocardiograms (ECGs), and vital signs
- Change in growth parameters
- Shifts from baseline in coagulation parameters (activated partial thromboplastin time [aPTT], prothrombin time [PT], and international normalized ratio [INR])
- Change in urine total protein
- Change from baseline in neurological examination outcomes
- The proportion of participants with a post-baseline platelet count below the lower limit of normal on at least 2 consecutive measurements
- The proportion of participants with a post-baseline QT interval using Fridericia's formula (QTcF) of > 500 msec and an increase from baseline to any post-baseline timepoint in QTcF of > 60 msec

#### **Study Secondary Objective (Part C)**

- To examine the clinical efficacy of nusinersen administered intrathecally at higher doses to participants with SMA.
- To examine the effect of nusinersen administered intrathecally at higher doses to participants with SMA

#### Study Secondary Endpoint (Part C)

- Change from baseline in Hammersmith Functional Motor Scale Expanded (HFMSE) score
- Change from baseline in Revised Upper Limb Module (RULM) score
- Total number of new World Health Organization (WHO) motor milestones
- Change from baseline in Assessment of Caregiver Experience with Neuromuscular Disease (ACEND)
- Change from baseline in Pediatric Quality of Life InventoryTM (PedsQL)

Product: Nusinersen	Statistical Analysis Plan
Study: 232SM203	Version: 1.0 Final

- Change from baseline in Children's Hospital of Philadelphia Infant Test of Neuromuscular Disorders (CHOP-INTEND) (Cohort 1 only)
- Change from baseline in Hammersmith Infant Neurological Examination (HINE) Section 2 motor milestones (Cohort 1 only)
- Number and duration of hospitalizations
- Clinical Global Impression of Change (CGIC) [physician, caregiver] at Day 302
- Number of serious respiratory events
- Ventilator use

# 2.2. Study Design

This 3-part study will evaluate the efficacy and safety of a higher dosing regimen of nusinersen in approximately 145 participants. The study will be conducted at approximately 65 sites

Product: Nusinersen	Statistical Analysis Plan
Study: 232SM203	Version: 1.0 Final

globally. Following the completion of this study, all eligible participants may elect to enrol in a separate long-term extension study (232SM302), pending study approval by ethics committees and the appropriate regulatory authorities. In regard to participants rolling over from Part B, this will be done without unblinding the participant's treatment group.

In Part C, up to approximately 40 participants who have already initiated treatment with nusinersen and have been receiving the approved dose of 12 mg for at least 1 year prior to entry will be enrolled in Part C. The initial cohort in Part C (i.e., Cohort 1) consists of up to approximately 20 participants of any age and of any SMA status. For Cohort 1, an attempt will be made to enroll at least 8 but no more than 12 participants  $\geq$  18 years of age (participants in Cohort 1 > 18 years of age must be ambulatory). Up to 5 participants with severe scoliosis and/or severe contractures may be enrolled in Cohort 1 of Part C after consultation with the Medical Monitor. An additional cohort (i.e., Cohort 2) consisting of up to approximately 20 adult participants ( $\geq$  18 years of age) was subsequently added to Part C in Protocol Version 5, in order to enable collection of data in adults transitioning from the currently approved nusinersen dosing regimen to a higher dose. Participants in Cohort 2 can be either ambulatory or non-ambulatory. All participants in Part C will receive a single bolus dose of 50 mg (which should be administered 4 months  $\pm$  14 days after their most recent maintenance dose of 12 mg) followed by 2 maintenance doses of 28 mg on Days 121 and 241. Participants in Part C will remain at the clinic for at least 24 hours after the first (bolus) dose for the purpose of completing study assessments.

#### 2.3. Sample Size Considerations

For Cohort 1 of Part C, an attempt was made to enroll at least 8 but no more than 12 participants  $\geq$  18 years of age (participants  $\geq$  18 years of age must be ambulatory). For Cohort 2 of Part C, all participants must be  $\geq$  18 years of age and can be either ambulatory or non-ambulatory.

# 2.4. General Trial Conduct Mitigation Strategy under COVID-19 Pandemic or humanitarian emergencies

In order to mitigate risk of missing dosing or assessments during the time of the COVID-19 pandemic, the following has been put into place:

- If a site is not closed due to COVID-19 or humanitarian emergencies and the site enables the participant to attend the visit in-clinic, then delayed visits within a reasonable timeframe are allowed.
- Site transfers are encouraged where possible, so that subjects can be transferred to another site for assessment. Instructions are in place to enable sites to do this including transfer of the database and source documents for the patient from the transferring site to the receiving site. This will allow the participant to receive dosing and protocol defined assessments to be made. Dosing can only be performed in the clinic setting due to intrathecal administration. In particular, if screening cannot be performed in the clinic, participants will be screened at a screening site and subsequently transferred to another

Product: Nusinersen	Statistical Analysis Plan
Study: 232SM203	Version: 1.0 Final

site to perform dosing and all assessments for the participant, since dosing can only be performed in the clinic setting due to intrathecal administration.

- A phone visit can be used to collect safety data (AEs, concomitant therapies/procedures)
- Transferring sites are encouraged to enter and clean all data before transferring the participant to the receiving site. The database for a participant will remain with the transferring site until data are entered and cleaned as much as possible, but the transferring site must have access to the participant in IRT and copies of all source documents. Any queries raised later on for data belonging to visits at the transferring site will be cleaned by the receiving site through the source documents, and interaction between monitors at the receiving and transferring sites. The transferring site will no longer have access to the database for a participant they have transferred, but the monitors will. The Subject ID will remain the same when a participant is transferred to another site, but the transfer site can be tracked via the Site ID.

#### 3. Definitions

#### 3.1. Dates and Points of Reference

In the remainder of this analysis plan only Part C analyses will be described. Separate SAPs will be developed for other parts of the study, (Parts A open label and B randomized double-blind). Therefore 'Part C' will not be stated throughout this document.

- Study Day 1: the date of the first dose of study treatment in 232SM203
- Study Day
  - o For a date on or after Study Day 1

Study Day = (Date of Interest) - (Study Day 1) + 1

• For a date before Study Day 1

```
Study Day = (Date of Interest) – (Study Day 1)
```

In order to distinguish nominal visit names from duration defined in days, visit names will be referred to as "Day 121", "Day 241", etc., and "121 days" or "241 days", etc. will be used to define time intervals.

Overall time on commercial nusinersen prior to first study dose= (Date of first study dose) – (Date of first commercial dose)

Overall time on study will be defined as the total number of days a participant is known to be followed on study calculated as follows:

```
Overall time on Study = (Last date on study) – (Date of first study dose) +1
```

Last date on study is defined as the date of the latest visit or evaluation or telephone contact, or time of death from all available data for a given participant.

Product: Nusinersen	Statistical Analysis Plan
Study: 232SM203	Version: 1.0 Final

Disease duration at informed consent is defined as time from age at symptom onset to age at informed consent.

#### **3.2.** Study Treatment

All participants will receive a single bolus dose of 50 mg of nusinersen administered intrathecally on Day 1 of this study (which should be administered 4 months  $\pm$  14 days after their most recent maintenance dose of 12 mg), followed by 2 maintenance doses of 28 mg of nusinersen on Days 121 and 241.

#### 3.3. Study Groups

All the summaries will be using display 'a' below, only selected analysis will be repeated using displays 'b' and 'c' and will include baseline characteristics, disposition, exposure, time on study incidence of adverse events and secondary endpoints.

a.

Nusinersen 50/28 mg			
Infantile-	Later-onset SMA		Total
onset SMA	Age < 18 years	Age>= 18 years	

b.

Nusinersen 50/28 mg					
No	on-Ambulator	y		Ambulatory	
Age <18 years	Age >=18	Total		Age>= 18	
	years		Age< 18 years	years	Total

c.

Nusinersen 50/28 mg					
< median time on commercial nusinersen >= median time on commercial nusinersen					
]	prior first do	se	pri	ior first dose	
Age <18 years	Age >=18	Total		Age >= 18	
	years		Age < 18 years	years	Total

#### 3.4. Study Periods

The total study duration for each participant will be a maximum of 323 to 382 days with 5 to 6 visits.

- Screening: 21 days
- Loading period: 1 day
- Maintenance period: 240 days

• Follow-up: 61 to 120 days

#### 3.5. Key Derived Variables

Not applicable.

#### 3.6. Stratification Factors and Subgroup Variables

#### **3.6.1.** Stratification Factors

Not applicable.

#### 3.6.2. Subgroup Variables

Not applicable.

#### 3.7. Analysis Sets

The Intent-to-Treat (ITT) Set is defined as all participants who receive at least one dose of nusinersen in 232SM203.

The Safety Analysis will be performed on the ITT Set.

A Per Protocol Set (PPS) will include the subset of the ITT Set who have no significant protocol deviations that would be expected to affect efficacy assessments

Significant protocol deviations will be determined prior to database lock and will include:

Participants with missing baseline results for the following assessments: HFMSE or RULM.

Participants who took experimental or approved agents for the treatment of SMA, including gene therapy, biological agent, any disease modifying therapy, or device, during the study. This includes marketed agents at experimental doses that are being tested for the treatment of SMA (oral albuterol/salbutamol, riluzole, carnitine, sodium phenylbutyrate, valproate, hydroxyurea, etc.).

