#### 5.6.4. Secondary Efficacy Endpoints

For each endpoint the main analysis will be performed on the ITT set and be repeated for PPS Set.

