#### 5.6.4.1. HFMSE

The HFMSE is a tool used to assess motor function in children 2 years or older with SMA. The scale was originally developed with 20 scored activities and was devised for use in children with Type 2 and Type 3 SMA with limited ambulation to give objective information on motor ability and clinical progression [Main 2003]. The expanded scale includes an additional module of 13 items developed to alleviate the ceiling effect and allow evaluation of higher functioning and ambulatory SMA patients [O'Hagen 2007]. Each item is scored 0 (unable), 1 (performs with modification or adaption) or 2 (able) and the total score is calculated by summing the 33 items and ranges from 0 to 66 with higher scores indicating greater motor function.

Product: Nusinersen	Statistical Analysis Plan
Study: 232SM203	Version: 1.0 Final

If 6 or fewer items are missing, then these items will be imputed to 0 when summing all 33 items. If greater than 6 items are missing, then the total score will be set to missing.

In order to further explore the response as measured by HFMSE score a number of thresholds will be evaluated: The proportion of subjects achieving: worsening of >= 4, >= 3, >=2, >=1 points, any worsening, no change (=0 points), any improvement, >=1, >=2, >=3, >=4 points improvement will be presented.

Analyses:

- Total score and change from baseline by visit
- Thresholds of change from baseline by visit
- Thresholds of change from baseline to last observed assessment
- Mean (-/+ SE) plots of total score and change from baseline over time

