#### **5.6.4.6. CHOP INTEND**

The CHOP INTEND test was specifically designed to evaluate the motor skills of infants with significant motor weakness, including infants with SMA [Glanzman 2010]. The CHOP INTEND test captures neck, trunk, and proximal and distal limb strength in 14 elicited and 2 observational items. The CHOP INTEND has been established as a safe and reliable infant motor measure in infantile-onset SMA and has been validated [Glanzman 2011].

The CHOP INTEND infant motor function scale is comprised of 16 test items, nine of which are scored 0, 1, 2, 3, or 4 with greater scores indicating greater muscle strength, five are scored as 0, 2, or 4, one is scored as 0, 1, 2, or 4, and one as 0, 2, 3, or 4. This can result in a worst possible total score of 0 to a best possible total score of 64. CHOP INTEND is used to assess spontaneous movement in the upper extremities, spontaneous movement in the lower extremities, hand grip, head in midline with visual stimulation, hip adductors, rolling elicited from the legs, rolling

Product: Nusinersen	Statistical Analysis Plan
Study: 232SM203	Version: 1.0 Final

elicited from the arms, shoulder and elbow flexion and horizontal abduction, shoulder flexion and elbow flexion, knee extension, hip flexion and foot dorsiflexion, head control, elbow flexion, neck flexion, head/neck extension, and spinal incurvation. CHOP INTEND is to be evaluated during the study for cohort 1. For each item, a score will be collected on the left and right side.

In order to examine if the response is consistent with a range of thresholds, the proportion of participants achieving: worsening of  $\geq=6$ ,  $\geq=5$ ,  $\geq=4$ ,  $\geq=3$ ,  $\geq=2$ ,  $\geq=1$  points, no change (=0 points), and improvement of  $\geq=1$ ,  $\geq=2$ ,  $\geq=3$ ,  $\geq=4$  (endpoint for main analysis),  $\geq=5$ ,  $\geq=6$  points will be presented. If a subject has moved scales and/or reached maximum score of 64 will be summarized on a different row in the tables.

Depending on data availability the following displays will be presented showing the following

- Total score and change from baseline by visit
- Thresholds of change from baseline by visit

#### 5.6.4.7. HINE Section 2

Hammersmith Infant Neurological Examination (HINE) is collected for cohort 1 infantile-onset SMA subjects, that are less than 2 years of age at the time of informed consent.

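### Part C Per Protocol Set: the exclusion for missing baseline HFMSE or RULM has no exemption where a scale does not apply, so the ordered PPS repeat of HINE Section 2 would have essentially no one in it

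*SAP*

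**What the plan says.** All references are to the Part C SAP unless stated.

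- **Section 3.7, Analysis Sets.** "A Per Protocol Set (PPS) will include the subset of the ITT Set who have no significant protocol deviations". Only deviations likely to bear on efficacy are meant. The first item on the list of such deviations is "Participants with missing baseline results for the following assessments: HFMSE or RULM". No age, cohort or not-applicable exemption is attached.
- **Section 5.6.4, Secondary Efficacy Endpoints.** "For each endpoint the main analysis will be performed on the ITT set and be repeated for PPS Set".
- **Section 5.6.4.1, HFMSE.** "The HFMSE is a tool used to assess motor function in children 2 years or older with SMA".
- **Section 5.6.4.7, HINE Section 2.** The examination "is collected for cohort 1 infantile-onset SMA subjects, that are less than 2 years of age at the time of informed consent". It is a listed secondary endpoint for Cohort 1.
- **Section 2.2, Study Design.** Cohort 1 takes up to "approximately 20 participants of any age and of any SMA status", so it has no lower age limit.
- **Section 5.6.2, Imputation.** A missing HFMSE or RULM baseline is not imputed.

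**The concern.** The PPS rule treats the absence of either of two motor scales as a fault, in a cohort whose motor scales depend partly on age. An infant for whom HFMSE is not an applicable instrument meets the exclusion as written although nothing went wrong. HINE Section 2 is collected only in such infants, so the rule and the instruction to repeat each endpoint in the PPS pull against each other.

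Two things are at stake. One ordered analysis could come out empty. The PPS repeats of endpoints that need neither HFMSE nor RULM (CHOP INTEND, hospitalizations, CGIC, serious respiratory events, ventilator use) could also become analyses of participants aged 2 and over, although the definition of the set does not say so.

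**Working it through.** The SAP gives no figure to reproduce here. The check is set logic on its own definitions.

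**Step 1. Who has HINE Section 2.** By 5.6.4.7: Cohort 1, infantile-onset, age < 2 years at consent. Call this set H.

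**Step 2. Who can be in the PPS.** By 3.7, missing HFMSE *or* missing RULM excludes. Membership therefore requires a baseline HFMSE *and* a baseline RULM, and lacking one of them is enough to be removed. Section 5.6.2 closes the route of imputing a missing baseline.

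**Step 3. Who has a baseline HFMSE.** By the description in 5.6.4.1: age ≥ 2 years. This is the one inferred step. The section describes the instrument and does not state a collection rule.

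**Step 4. Overlap.** H ∩ PPS ⊆ {age < 2 at consent} ∩ {baseline HFMSE present, age ≥ 2}. This is empty however many infants enrol, with one exception. Section 3.4 allows 21 days of screening, so a child just under 2 at consent could turn 2 and have both scales done before the first dose. Hence essentially no one, rather than strictly zero. RULM is not needed for this result.

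**Step 5. How many infants.** The SAP gives no number. Section 5.7.3.1 expects few participants under 2. Section 2.2 requires at least 1 year on 12 mg before entry, so a child under 24 months at consent must have started treatment before 24 − 12 = 12 months of age. The number lies between zero and a small part of the roughly 20 places in Cohort 1.

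**Step 6. The effect of the *or* at any age.**

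| Baseline HFMSE | Baseline RULM | In PPS under 3.7 | Measured scale lost from its own PPS analysis |
|---|---|---|---|
| present | present | yes | none |
| present | missing | no | HFMSE |
| missing | present | no | RULM |
| missing | missing | no | neither was measured |

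The middle rows do not depend on the age assumption. Because a missing baseline is not imputed, a participant without a baseline HFMSE has no change from baseline in HFMSE in the ITT set either. For change from baseline, then, the exclusion matters mainly for the *other* endpoints, where the missing scale is not needed.

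**The case against.** The strongest reply is that the age premise is not written down. Where this SAP limits an assessment by age it says so: PedsQL (5.6.4.4), ACEND (5.6.4.5), HINE Section 2 (5.6.4.7) and HINE Sections 1 and 3 (5.7.3.1). The Part C HFMSE and RULM sections contain no collection limit, and the only age range for RULM is a descriptive remark in the Part A SAP. The schedule belongs to the protocol, which was not available. This stands, and the conclusion about infants is conditional on it.

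Second, the exclusions are meant to be significant deviations, settled before database lock. An assessment that was never scheduled is not naturally a deviation, and *missing* may mean required but not obtained. On that reading the infants stay in the PPS and the conflict disappears. This is reasonable and may be what was intended, but 3.7 does not say it, and a programmer applying the listed item literally would exclude them.

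Third, one common PPS for all endpoints is a legitimate convention, the HINE Section 2 displays are already conditional on data being available, and display *a* in section 3.3 gives infantile-onset SMA its own column. These points limit the harm. They do not make the rule fit the population.

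A reader might also infer that infants would be reported as deviators in the deviation tables. The SAP does not support that. Section 5.4 draws deviations from those found at site monitoring, and nothing there has a monitor log an assessment that was not due.

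**Conclusion.** The rule in 3.7 misfires as written. Assuming HFMSE is not done below age 2, a literal reading leaves essentially no one in the PPS repeat of HINE Section 2 and removes the same infants from the PPS repeats of CHOP INTEND and the other endpoints. Independently of that assumption, the *or* removes participants from the PPS analysis of a scale on which they have a valid baseline.

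The size is modest. The infants concerned are few and may be none. Part C efficacy is secondary and descriptive, with no hypothesis test in 5.6.4; the main efficacy analysis uses the ITT set, and safety is analysed on the ITT set too. Only a supportive repeat is affected.

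A reader might go further and say that every participant under 2 is certainly excluded and that the HINE Section 2 repeat certainly has N = 0. The document does not carry that. It gives no collection rule for HFMSE or RULM by age, and the child who turns 2 during screening is an exception.

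**What to change.** In section 3.7, make the criterion specific to the endpoint: a participant is left out of the PPS analysis of a given scale only if that scale was scheduled for the participant and its baseline is missing. Add that a scale not scheduled for a participant is not a protocol deviation. For endpoints that use neither HFMSE nor RULM, a missing baseline on those scales should not exclude anyone.

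Tie the wording to what was scheduled rather than to a new age cut-off. In particular, do not set an age limit for CHOP INTEND: section 5.6.4.6 assigns it to Cohort 1 without one.

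The cost is a sentence or two in 3.7 and a PPS flag per endpoint in the analysis datasets, with no new data. The downside is that PPS membership then differs between endpoints, so each PPS table must state its own denominator.
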